 - The subject must have been diagnosed with episodic migraine headache at least six months prior to entering into the Study, consistent with the International Headache Classification of Headache Disorders (ICHD-II and ICHD-III beta) guidelines.
 - The subject must have a history of at least three consecutive months of stable migraine headaches prior to entering the study. The subjects will not have had changes in medication usage (prescription medications for migraine headache) for the three months leading up to the study, nor will they introduce new medications during the study period. (The primary focus is on prescription medications for migraine headache. However, medications that are prescribed for co-morbid conditions which also have

demonstrated efficacy for migraine prevention should not be altered in this time period.)

- Subjects will satisfy these criteria: On a monthly basis, at least four, and not more than a total of fourteen (4-14), headache days of which between four and fourteen (4-14) are migraine headache days, as judged by the subject.
- The subject must not have failed on more than two classes of properly administered prophylactic pharmaceutical therapies for migraine headache. The subject may be on a single migraine prophylactic drug as long as the dosage has not been altered within three months of starting the study and the dosage must not be altered for the duration of the study;
- The Investigator must have confidence in the subject's ability to reliably use the CVS device and promptly complete the electronic daily headache diary forms. The daily headache diary will be completed from the beginning of the pre-treatment baseline period through the end of the study. The diary is described more fully below and in the definitions section at the end of this document.

• **Exclusion Criteria:** Individuals who:

- have previously participated in a clinical trial using the CVS Device
- are pregnant
- using more than one concurrent prophylactic pharmaceutical therapy for migraine headache
- have a history of cardiovascular disease
- work night shifts
- have been diagnosed with vestibular migraine
- have menstrual migraine exclusively
- have been diagnosed with post-traumatic migraine
- have a history of unstable mood disorder or unstable anxiety disorder. Specifically, a BDI-II score of 20 or greater and/or a BAI score of 16 or greater will disqualify a patient from randomizing into the treatment portion of the study.
- use a hearing aid

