If the subject is discontinued from the participation in the study for any reason, the principal investigator must make every effort to perform all evaluations for the final visit and document the reasons for discontinuation. If a subject withdraws due to an adverse event, the study coordinator will follow up with regular phone calls to document the resolution of the event.

Though a subject will not be withdrawn from the study if she/he exceeds 14 headache days in any of the treatment months, such subjects will be grouped separately during the final study analysis. The rationale for this grouping is that a large percentage of subjects in the first CVS migraine RCT were excluded from randomization because they exceeded 14 headache days, thus calling into question their stable episodic status. If a subject has a “good month” during baseline, but is potentially unstable, she/he might be recruited into the study in violation of the aim of enrolling stable EM subjects. No evidence that the CVS device increased headache burden was seen in the first RCT. However, we will continue to follow subjects who exceed 14 headache days in a month during the treatment period so as to gather more data on this sub-population.

- **Concomitant Medications**

- The use of acute abortive medications for the symptomatic treatment of migraine headache will be allowed during the clinical trial. Subjects may use their usual acute abortive medications, and medications should not be changed during the clinical trial. A treated migraine headache is one for which a subject has taken an acute abortive medication (prescription medication, not OTC).
- The subject may be on a single migraine prophylactic drug as long as the dosage has not been altered within three months of starting the study and the dosage must not be altered for the duration of the study. The subject must not have failed on more than two classes of properly administered prophylactic pharmaceutical therapies for migraine headache. Prophylactic medications used to treat other medical conditions may be used, at the principal investigator's discretion, if the subject is taking a stable dose for at least three months prior to screening and continues throughout the study.

3) Pivotal Study Size; Randomization

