- (i) **Screening & Baseline Period:** Once the subject has been established as having the appropriate pre-treatment history, she/he will be asked to complete a review of the informed consent. If the subject agrees to participate in the study, the subject will then complete a screening visit. The study coordinator will complete a headache history questionnaire for the subject. If the subject is recommended for continuation in the study after the screening visit and tentatively approved by a principal investigator, she/he will start a daily headache diary and continue to make entries for twenty-eight consecutive days. Subjects will be given Scion email accounts to be used for submitting headache diary entries. Sites will assist subjects with syncing their Scion email accounts with their smartphones or tablets, and will ensure that subjects can competently take a photo of the ediary form, upload and send according to procedure. If the subject does not complete at least 25 of 28 daily headache diary entries during the baseline period, she or he will be withdrawn and will not proceed to randomization.
- (ii) **Clinic Training Visit:** After enrollment, the completion of one month of daily headache diary entries, and reconfirmation by the relevant investigator of the subject's participation in the study, the subject will come to the clinic for an appointment(s) for training on the use of the CVS device. During the clinic visit, the subject will complete a quality of life (QOL) assessment. The assessment will consist of the HIT-6, BAI, BDI-II and Pittsburgh Sleep Quality Assessment questionnaires. The BAI and BDI-II scores will be tallied with the following outcomes:
 - a. Subjects who score 20 or higher on the BDI-II or answer affirmative to questions 9 on the BDI-form will not proceed to randomization and will be withdrawn from the study.
 - b. Subjects who score 16 or higher on the Beck Anxiety Index will not proceed to randomization and will be withdrawn from the study.

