PROTOCOL NUMBER: _____**Treatment Day 1 (Visit 2)****Baseline Daily Headache Diary:****Yes** **No**

Does the subject have on a monthly basis, at least four, and not more than a total of fourteen (4-14), headache days of which between four and fourteen (4-14) are migraine headache days, as judged by the subject.		
If Yes , please proceed with Treatment Day 1 Visit procedures. If No , please conclude the visit, and complete the Subject Disposition Form. Subject is a Screen Failure.		

Adverse Events and Concomitant Medication Assessment:**Yes** **No**

Any Adverse Events (AEs) since last visit?		
If Yes , please complete AE form.		
Any new medications or changes in medications since last visit?		
If Yes , please add medication(s) to the Concomitant Medication form. Acute abortive medications and migraine prophylactic medications should not be changed during the clinical trial.		

Vital Signs:

Height:	_____ cm / inches (circle one)
Weight:	_____ kg / lbs (circle one)

Urine Pregnancy Test Results:**Positive** **Negative** **N/A**

Name:	Lot #:	Exp. Date:			
-------	--------	------------	--------------------------	--------------------------	--------------------------

Ear Exam: Observations and check for presence of cerumen (recommend cleaning procedure as needed). _____

Physician Signature (for ear exam): _____ **Date:** _____

Quality of Life Assessments:**Yes** **No****Scores**

Hit-6 Questionnaire (completed)			
Pittsburgh Sleep Quality Assessment (completed)			
BDI-II (completed)			
BAI (completed)			
A BDI-II score of 20 or greater and/or a BAI score of 16 or greater will disqualify a patient from randomizing into the treatment portion of the study.			

Randomization:**Yes** **No**

Does the subject met all eligibility criteria for randomization?		

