If Yes , please proceed with Device Treatment Training. If No , please conclude the visit, and complete the Subject Disposition Form. Subject is a Screen Failure.		

SUBJECT ID: _____
DATE: _____SITE #: _____
PROTOCOL NUMBER: _____**Device Treatment at the Clinical Site:****Yes** **No**

Any side effects or AEs reported after device treatment?		
Was the device treatment aborted?		
Any complaints from subject?		
Any concerns about the subject?		
If Yes, to any questions above, please provide comment:		

- Dispense TNM Device to subject.
- Review device compliance and proper operation of the device and delivery of treatments.
- Administer Usability Questionnaire after completion of device training.
- Review Daily Headache Diary completion and upload to gmail account each day.

Study Coordinator: *I verify that the subject has received training and has shown competence in using the TNM Device. I believe that the subject will be able to complete device treatments in the home setting. I have confirmed with the subject that he/she will contact me regarding any future questions regarding safe use of the TNM device, should they arise.*

Study Coordinator Signature_____
Date

I have reviewed the data from this visit and found the information to be complete and accurate. I verify that all of the tasks have been performed.

Principal Investigator Signature_____
Date

SUBJECT ID: _____
DATE: _____SITE #: _____
PROTOCOL NUMBER: _____**Clinic Visit Day 14 (Visit 3)****Adverse Events and Concomitant Medication Assessment:** Yes No

Any Adverse Events (AEs) since last visit?		
If Yes, please complete AE form.		
Any new medications or changes in medications since last visit?		
If Yes, please add medication(s) to the Concomitant Medication form. Acute abortive medications and migraine prophylactic medications should not be changed during the clinical trial.		

Ear Exam: Observations and check for presence of cerumen (recommend cleaning procedure as needed). _____

Physician Signature (for ear exam): _____ **Date:** _____

Vital Signs:

Height:	_____ cm / inches
Weight:	_____ kg / lbs

Device Treatment at the Clinical Site:

Yes No

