- Review Daily Headache Diary completion and upload to gmail account each day.
- Remind subject of the **Final Study Visit** (end of Week 40) scheduled on ____/____/____.

Study Coordinator Signature

Date

SUBJECT ID: _____
DATE: _____SITE #: _____
PROTOCOL NUMBER: _____**Final Study Visit**
(Visit 6-End of Week 40)

Adverse Events and Concomitant Medication Assessment:	Yes	No
Any Adverse Events (AEs) since last visit?		
If Yes, please complete AE form.		
Any new medications or changes in medications since last visit?		
If Yes, please add medication(s) to the Concomitant Medication form. Acute abortive medications and migraine prophylactic medications should not be changed during the clinical trial.		

Vital Signs:

Height:	_____ cm / inches (circle one)
Weight:	_____ kg / lbs (circle one)

Ear Exam: Observations and check for presence of cerumen (recommend cleaning procedure as needed). _____

Physician Signature (for ear exam): _____ **Date:** _____

Quality of Life Assessments:	Yes	No	Scores
Hit-6 Questionnaire (completed)			
Pittsburgh Sleep Quality Assessment (completed)			
BDI-II (completed)			
BAI (completed)			
BDI-II scores above 20 or BAI scores above 16 after treatment has commenced should be referred to the PI for consultation with [name]. If the subject answers in the affirmative to question 9 of the BDI-II form, he/she should be referred for mental health counseling on that same clinic visit.			

- Complete Subject Disposition Form (Subject Status=Completed)

I have reviewed the data from this visit and found the information to be complete and accurate. I verify that all of the tasks have been performed.

Principal Investigator Signature

Date

SUBJECT ID: _____
DATE: _____

SITE #: _____
PROTOCOL NUMBER: _____

Subject Disposition Form

Select the Subject's Status for the Study: **Excluded** (select reason below)

- Screen Failure
- Physician Decision

Discontinued (select reason below)

- Adverse Event
- Protocol Violation
- Withdrawal by Subject
- Physician Decision
- Lost to Follow-up
- Lack of Efficacy
- Study Terminated by Sponsor
- Lack of Qualifying Event

Completed

Comments: _____

Study Coordinator Signature

Date

Principal Investigator Signature

Date

SUBJECT ID: _____
DATE: _____SITE #: _____
PROTOCOL NUMBER: _____**Early Termination Visit****Adverse Events and Concomitant Medication Assessment:****Yes No**

Any Adverse Events (AEs) since last visit?		

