If Yes , please complete AE form.		
Any new medications or changes in medications since last visit?		
If Yes , please add medication(s) to the Concomitant Medication form. Acute abortive medications and migraine prophylactic medications should not be changed during the clinical trial.		

Vital Signs:

Height:	_____ cm / inches (circle one)
Weight:	_____ kg / lbs (circle one)

Ear Exam: Observations and check for presence of cerumen (recommend cleaning procedure as needed). _____

Physician Signature (for ear exam): _____ **Date:** _____

Quality of Life Assessments:**Yes No****Scores**

Hit-6 Questionnaire (completed)			
Pittsburgh Sleep Quality Assessment (completed)			
BDI-II (completed)			
BAI (completed)			
BDI-II scores above 20 or BAI scores above 16 after treatment has commenced should be referred to the PI for consultation with [name]. If the subject answers in the affirmative to question 9 of the BDI-II form, he/she should be referred for mental health counseling on that same clinic visit.			

- Complete Subject Disposition Form (Subject Status=Discontinued; select reason)
- Return device and study related materials, as needed.

I have reviewed the data from this visit and found the information to be complete and accurate. I verify that all of the tasks have been performed.

Principal Investigator Signature

Date

The following questionnaires are to be completed by the study patients in accordance with establishing the acceptance criteria set forth in the usability validation plan (*PLN-04-ENG-004-SN, section 11). Questionnaires will be completed at the end of the training period, once a treatment is completed, at the 2-week clinic visit, and at the end of the first and second treatment periods. The following acceptance criteria will be addressed during the evaluation periods:

- At the completion of training:
 - Device comfort, ease of use, intuitive nature of GUI, ability to hear alarm, identification of labeling, etc.
- At the 2-week clinic visit:
 - Device comfort, ease of use, device cleaning, device storage, treatment protocol
- End of the study periods

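### An affirmative BDI-II item 9 bars randomisation in Section 4, but the exclusion criterion and the Visit 2 form omit it, and Visit 2 states no same-visit referral

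*Combined protocol and SAP*

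**What the plan says.** Section 4, item (ii) Clinic Training Visit, sets two separate BDI-II stops before randomisation. One is a total of 20 or more. The other applies to subjects who "answer affirmative to questions 9 on the BDI-form will not proceed to randomization". Either one leads to withdrawal, and so does a BAI of 16 or more.

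The Exclusion Criteria in Section 2 carry only the scores: "Specifically, a BDI-II score of 20 or greater and/or a BAI score of 16 or greater will disqualify a patient from randomizing". The Treatment Day 1 (Visit 2) form repeats this under Quality of Life Assessments: "A BDI-II score of 20 or greater and/or a BAI score of 16 or greater will disqualify a patient from randomizing". Just below, the form asks a general question, "Does the subject met all eligibility criteria for randomization". If the answer is no, the instruction is: "please conclude the visit, and complete the Subject Disposition Form. Subject is a Screen Failure".

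The same-visit referral for mental health counselling after an affirmative item 9 appears in Section 10, under a heading limited to mood abnormality after randomisation. It is repeated on the Visit 4, Visit 5, Visit 6 and Early Termination forms.

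**The concern.** The rule that matters most for safety stands in one place only, and the two places a site would consult to decide eligibility leave it out. The Section 2 criterion introduces its cut-offs as the specific definition of the exclusion, so it reads as complete. The Visit 2 form has a score field for the BDI-II but no item 9 check.

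Two failures are possible. A site working from the form could randomise a subject whom Section 4 bars. Or a site that correctly stops such a subject could end the visit without the referral that the later forms call for. Sites randomise individually from envelopes (Section 3), and no central step is described that would catch the first failure. The stakes are participant safety and uniform eligibility across sites; alpha, power and the primary analysis are not involved.

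**Working it through.** The plan gives no figure to reproduce here. The check compares the texts, with a little arithmetic on the BDI-II score.

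**Step 1. The stopping rule in each place**

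| Place | BDI-II total | BAI | Item 9 |
|---|---|---|---|
| Section 4, item (ii) | 20 or more | 16 or more | any affirmative answer |
| Section 2, Exclusion Criteria | 20 or more | 16 or more | not named |
| Visit 1 exclusion checklist | none given | none given | not named |
| Visit 2 form | 20 or more | 16 or more | not named |

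**Step 2. Does the total score cover item 9?** Inputs from the BDI-II form: 21 items, each scored 0 to 3, with affirmative answers to item 9 scoring *s* = 1, 2 or 3. Let *R* be the sum of the other 20 items, so the total is *T* = *s* + *R*. The score rule catches the subject only if *T* ≥ 20, that is, *R* ≥ 20 − *s*. The totals that escape run from *s* to 19.

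| *s* | *R* needed (20 − *s*) | Mean per other item (*R*/20) | Totals not caught | Number of totals (20 − *s*) |
|---|---|---|---|---|
| 1 | 19 | 0.95 | 1 to 19 | 19 |
| 2 | 18 | 0.90 | 2 to 19 | 18 |
| 3 | 17 | 0.85 | 3 to 19 | 17 |

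The Definitions place totals of 0 to 13 in the minimal band. A subject with *s* = 1 and *R* ≤ 12 is in that band while reporting suicidal thoughts. The total is therefore no substitute for item 9. These counts show which scores escape the printed rule; they do not say how often such scores occur.

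**Step 3. Which forms carry the referral**

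| Form collecting the BDI-II | Item 9 same-visit referral |
|---|---|
| Visit 2 (decides randomisation) | no |
| Visit 4 (end of week 16) | yes |
| Visit 5 (end of week 28) | yes |
| Visit 6 (end of week 40) | yes |
| Early Termination | yes |

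Four of five forms carry it. The one that does not is the only one that decides randomisation.

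**Step 4. Where a subject stopped at Visit 2 is sent.** Section 4 says only that the subject is withdrawn. The Visit 2 form ends the visit and records a screen failure. On the Subject Disposition Form that reason sits under the first status, "Select the Subject's Status for the Study: Excluded (select reason below". The Early Termination form, which has the referral, belongs to the other status: "Complete Subject Disposition Form (Subject Status=Discontinued; select reason". Nothing on the Visit 2 form leads from one to the other.

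**Step 5. Time to the next BDI-II after a randomisation in error.** Visit 2 opens week 5 and Visit 4 closes week 16: (16 − 5 + 1) × 7 = 84 days. Five contacts fall in between: the week 7 visit and the phone contacts at weeks 9, 11, 13 and 15. All five ask about adverse events and medication. The week 7 form also asks whether there are concerns about the subject, and Section 4, item (iv) sends safety concerns at that visit to the principal investigator. None repeats the BDI-II or names item 9.

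**The case against.** The strongest reply is that nothing here is contradictory. Section 4 is the operative text for the visit where the BDI-II is first given, and it is clear. The Section 2 criterion and the form say that certain scores disqualify; neither says that only those scores do. The form's general eligibility question takes in Section 4, and the forms abbreviate the protocol elsewhere: the Visit 2 diary check, for instance, omits the rule of 25 entries in 28 days. The principal investigator also signs that the visit's data were reviewed, and the form asks about concerns after the first device treatment. All of this stands. The rules can be obeyed together, so the fault is an omission. But the general question follows a specific and incomplete rule, the eligibility list it points to has the same gap, and the question about concerns comes after randomisation.

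On referral, the Withdrawal Criteria include a pre-randomisation event (too few baseline diary entries), so that section can cover subjects never randomised. On discontinuation for any reason, it says that "the principal investigator must make every effort to perform all evaluations for the final visit". The schedule puts the final and early termination visits in one column, and the item 9 sentence on the Early Termination form is not limited to treated subjects. This route is arguable. It still depends on an inference that the Visit 2 form does not prompt, and that its screen-failure label points away from.

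Two further points are fair. The later forms say that the subject should be referred, which is weaker than a requirement. And the exclusion for unstable mood disorder narrows the pool of affected subjects by an unknown amount.

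**Conclusion.** The concern holds, as an incomplete criterion and form. A subject with item 9 scored 1 to 3, a BDI-II total of no more than 19 and a BAI of 0 to 15 passes every cut-off printed in Section 2 and on the Visit 2 form, yet Section 4 bars that subject. Same-visit referral at Visit 2 is not stated and is at best unclear. The number of subjects affected cannot be derived from the documents, and none is assumed.

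The first failure requires staff to work from the form and the exclusion list without also applying Section 4. The second requires them to follow the form's close-out literally, although clinical judgement may lead them to refer anyway. Neither has any bearing on sample size, error rates or the primary comparison. The point should be corrected because it concerns suicidal thoughts and because the sponsor's later forms already call for same-visit referral; nothing in the documents explains why Visit 2 differs.

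**What to change.** 1. In the Section 2 exclusion criterion, add: *or a score of 1 or more on BDI-II item 9*.
2. On the Visit 2 form, add the same condition as its own Yes/No check, placed before the randomisation question.
3. In Section 4, item (ii), and on the Visit 2 form, state that a positive item 9 leads to mental health referral at that visit, before the subject is closed out as a screen failure. The referral sentence on the Visit 4 form can be reused.

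The cost is a few lines in two places in the protocol and one case report form. Sample size, visit schedule and analysis do not change.

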The design size contemplates enrolling up to one hundred and twenty (120) subjects who will successfully follow through to completion of their participation in at least the first treatment portion of the study (first 3-month treatment period). The subjects will be randomly assigned to: twice-per-day active, once-per-day active or twice-per-day placebo in a 1:1:1 ratio.

The results of the first migraine RCT did not show evidence of stratification based on gender or clinical site or baseline headache frequency. Envelopes containing

randomization assignments will be grouped in batches of six, each batch containing two of each of the three assignment arms. The batches of envelopes will be randomly shuffled by an agent not involved with the study. A given batch will be completed before the next batch is opened. This procedure results in 20 possible different arrangements, for six subjects, of the ordering of treatment and placebo assignments. The unblinded coordinator will record the subject's designation but will not share the assignment with the subject, principal investigator, or statistician. Each study site will be individually randomized (no central randomization).

The assessment of the primary endpoint will be completed by a blinded, central statistician. The subjects will be told, within the informed consent document, of the existence of a placebo arm. Subjects will be told that the device stimulates the brain stem. Subjects will be told that they will receive at least 3-months of active treatment during the 6-month treatment period. In fact, subjects in the placebo arm in the first 3-month period will be switched to active in the second 3-month period. Subjects will be asked to guess (and provide reasons) about their treatment assignment at the end of the first 3-month treatment period and at the end of the second 3-month treatment period. Subjects will also be asked, after their very first treatment in the clinic, a series of questions designed to assess the quality of blinding (to provide evidence that the placebo device is an effective sham).

4) Study Schedule; Subject Enrollment and Activities

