- (iii) Also, women of childbearing age will complete a urine-based pregnancy test to reconfirm that they are not pregnant. The unblinded coordinator will open, at random, an envelope assigning the subject to one of the three study arms. The clinic period is described below. During the first visit, the subject will complete a training session based on a set training module. The subject will complete a proficiency evaluation and the study coordinator will certify the subject's proficiency in the use of the CVS device. The study coordinator will

complete a visit assessment form. At the end of training, a first usability questionnaire will be completed by the subject.

(iv) **First Treatment Period:** The eighty-four days (3 months) following the pre-treatment baseline period constitute the first treatment period. This is the test period, the results from which will be measured against the pre-treatment baseline period data in assessing the study endpoints. Specifically, data from the last month of the first treatment period will be compared with the one-month-long pre-treatment baseline period. As close as possible (as scheduling permits) to two weeks after the start of treatment, a clinical visit will occur and another visit assessment form will be completed. A second usability questionnaire will be completed. The subject will be asked to bring the CVS device to the clinic to perform a treatment in front of the unblinded study coordinator to reaffirm proficiency in using the device. Any issues related to balance or other safety concerns will promptly be referred to the site principal investigator, who can terminate the subject's further participation in the study if necessary.

(v) **End of First Treatment Period – Start of Second Treatment Period:** At the end of the first treatment period the subject will be asked to return to the clinic and will be asked to complete the QOL questionnaires and a third usability questionnaire. All subjects will receive new SD cards for the second treatment period and the old SD cards will be retained so that treatment compliance logs can be extracted. All subjects will receive active treatment cards with the following assignments (first treatment period -> second treatment period):

- BID placebo -> BID active
- BID active -> BID active
- QD active -> QD active

Subjects will perform a treatment in front of the unblinded coordinator to re- confirm their ability to properly use the device.

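### Site-level batches of six, opened by an unblinded coordinator with no fixed envelope order, could let that coordinator know up to 20% of assignments in advance; the stated count of 20 orderings should be 90

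*Combined protocol and SAP*

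**What the plan says.** Section 3 (Pivotal Study Size; Randomization) allocates subjects to "twice-per-day active, once-per-day active or twice-per-day placebo in a 1:1:1 ratio". Envelopes carrying "randomization assignments will be grouped in batches of six, each batch containing two of each of the three assignment arms" are used at each site, without central randomisation. On order and use it says "The batches of envelopes will be randomly shuffled by an agent not involved with the study" and "A given batch will be completed before the next batch is opened". It then gives a count: "This procedure results in 20 possible different arrangements, for six subjects, of the ordering of treatment and placebo assignments".

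On who knows what, the same section says "The unblinded coordinator will record the subject's designation but will not share the assignment with the subject, principal investigator, or statistician".

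Section 4 (Study Schedule; Subject Enrollment and Activities), item (iii), describes the act of allocation: "The unblinded coordinator will open, at random, an envelope assigning the subject to one of the three study arms". Section 2 (Subject Selection Criteria) has investigators identify and screen candidates together with, and through, their coordinators.

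The protocol does not mention numbered envelopes, a varying batch size, or any rule that keeps the person opening envelopes out of recruitment.

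**The concern.** The size and content of a batch are printed in the protocol, and the role that records past assignments also opens the next envelope. Near the end of a batch that person can work out what remains. Concealment then depends on the coordinator not acting on the knowledge, for example by moving a visit or by encouraging or discouraging a candidate still in screening. The primary outcome rests on the subject's own classification of migraine, so a difference between arms in who enters could carry into the comparison.

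There is also an audit gap. Section 3 relies on a shuffle by an uninvolved agent, while item (iii) of section 4 lets the coordinator pick an envelope. Without a numbered sequence, nobody can later show that envelopes were taken in a pre-set order. The stated number of orderings also does not fit a three-arm batch.

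**Working it through.** **Inputs, all from section 3:** three arms at 1:1:1; batch of six with two per arm; batches used up in turn; randomisation by site; target of 120 subjects. The number of sites is not given and is varied below as an assumption.

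**1. The plan's own figure (20 orderings).**
- Three arms, 2:2:2: 6!/(2!·2!·2!) = 720/8 = 90.
- Both active arms merged, four active and two placebo: C(6,2) = 15.
- Two arms, 3:3: C(6,3) = 20.

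The figure of 20 is not reproduced for this design. Of the designs tried, only a two-arm 3:3 batch gives it. The number of batches, 120/6, is also 20, but the sentence counts arrangements for six subjects, so that does not explain it.

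**2. Assignments known with certainty.** An assignment is certain when all envelopes left in the batch are for one arm.
- Positions 1 to 4: never, because at least three envelopes remain and each arm has only two.
- Position 5: the last two envelopes match in 18 of 90 orderings, so 1/5.
- Position 6: always.

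Expected number per batch: 1/5 + 1 = 1.2. Share: 1.2/6 = 20%. Over 120 subjects in complete batches: 0.20 × 120 = 24.

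**3. Best guess.** The chance that the likeliest remaining arm is correct, by position:

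| Position | 1 | 2 | 3 | 4 | 5 | 6 |
|---|---|---|---|---|---|---|
| Probability | 0.333 | 0.400 | 0.500 | 0.533 | 0.600 | 1.000 |

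The sum is 3.367, and 3.367/6 = 56.1%, against 33.3% with no information.

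**4. Unfinished last batches.** With equal sites (assumed):
- 24 per site (5 sites): four full batches, 4 × 1.2/24 = 20%.
- 40 per site (3 sites): six full batches plus four subjects, 6 × 1.2/40 = 18%.
- 15 per site (8 sites): two full batches plus three subjects, 2 × 1.2/15 = 16%.
- 10 per site (12 sites): one full batch plus four subjects, 1.2/10 = 12%.

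The best-guess rate falls too: at 10 per site it is (3.367 + 0.333 + 0.400 + 0.500 + 0.533)/10 = 51%.

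**5. Mixed batches of 6 and 9.** This was simulated with equal mixing and 24 subjects per site. The guesser knows that both sizes are possible and sees every earlier assignment, but does not know which size is in use. Certain knowledge falls from about 20% to about 5%. Best-guess accuracy falls only from about 56% to about 53%.

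**6. Picking at random against opening in order.** A random draw from a balanced batch has the same distribution as a shuffled fixed order, so the figures in steps 2 and 3 are the same either way. What differs is whether a sequence exists to check against.

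**The case against.** The strongest reply is that the people who exercise judgement about entry do not see assignments. Section 2 gives confidence in the subject's ability to use the device to the investigator. Section 4 gives reconfirmation of participation to the investigator and places it before the training visit. Section 3 withholds assignments from that role. Most checks at the randomisation visit are numeric: diary completeness, headache-day counts, mood-score cut-offs and a pregnancy test. Judgement-based screening comes at least 28 days earlier, when the next envelope is hard to foresee. This stands. A reader might infer that investigators' entry decisions are open to the next assignment; the documents do not support that.

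It is also fair to say that knowledge of all earlier assignments is inferred. It assumes one coordinator, or a shared log, per site. The protocol uses both study coordinator and unblinded coordinator without saying whether they are the same person.

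A reader might further infer that opening an envelope at random creates the predictability. It does not: the fixed batch does (step 6).

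What survives is narrower. Coordinators take part in screening under section 2, nothing separates the envelope opener from that work, and visit dates can move. On the Treatment Day 1 (Visit 2) form the eligibility question comes before device training, but the investigator's signature line comes at the end, after the device treatment. The protocol therefore does not show a signed eligibility decision before the envelope is opened.

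**Conclusion.** The point holds as a modest weakness in allocation concealment that is cheap to remove. Up to 20% of assignments could be known to the unblinded coordinator in advance, and up to 56% guessed correctly. Both are ceilings for complete batches. They assume that the coordinator knows the batch make-up and all earlier assignments at the site. With 1 to 12 equal sites, the certain share runs from 12% to 20%.

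The figures measure opportunity. They do not show that bias would occur, and no effect on the primary estimate can be calculated from the documents. The route is the coordinator's part in screening and scheduling.

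The count of 20 is wrong, and 90 is right for this batch. A reader might take the error as a sign that the randomisation itself is faulty. It is descriptive only: the batch content is stated correctly, and neither the 1:1:1 ratio nor the sample size depends on the count. It suggests wording carried over from a two-arm design but does not prove it.

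**What to change.** - Have the uninvolved agent prepare sealed, opaque, sequentially numbered envelopes for each site. Open them strictly in order, and only after the investigator has signed and dated eligibility. Move that signature on the Visit 2 form ahead of randomisation. This is the main remedy, because mixed batch sizes alone leave the best guess at about 53%.
- Delete *at random* from item (iii) of section 4 and refer to the numbered order, so that sections 3 and 4 agree on who sets the sequence.
- Use mixed batch sizes, for example 6 and 9, and leave the sizes out of any text that sites see.
- State whether the person opening envelopes takes part in recruitment or scheduling.
- Correct 20 to 90 if fixed batches of six are kept; otherwise delete the count.

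The cost is new envelope sets, a few sentences and one form change. The statistical price is slightly larger possible imbalance within a site: in an unfinished batch two arms can differ by up to 3 subjects with batches of nine, against 2 with batches of six.
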